# 2.3.3.2 Preclinical Toxicology

General toxicology studies for ISIS 703802 consisted of sub-chronic (16-week) and chronic (26- or 39week) toxicity studies CD-1 in mice and cynomolgus monkeys. Since ISIS 703802 is not fully complementary to the mouse ANGPTL3 transcript, treatment group receiving a mouse-specific inhibitor (ISIS 731875) was also included in the mouse study. Please refer to the Investigator Brochure for a detailed description of the preclinical toxicology and pharmacokinetics with ISIS 703802.

Pharmacokinetic data confirmed continuous and dose-dependent exposure to ISIS 703802. An estimated liver and plasma terminal elimination half-life values of approximately 1 week and 3-4 weeks for 2 mg/kg and 35 mg/kg, respectively, were observed in monkeys. The most noteworthy findings observed in mice and monkeys following ISIS 703802 treatment were, in general, non-specific class effects related to the uptake and accumulation of ASO and no toxicologically relevant findings were considered related to the pharmacologic inhibition of hepatic ANGPTL3 expression, either with the present series of studies or with the former development candidate targeting ANGPTL3. There were no test-article related changes in PLT count in either mouse or monkey in both sub-chronic and chronic studies.

The most noteworthy finding in the monkey was the kidney alteration (hypoalbuminemia and proteinuria) seen in one early-sacrifice animal from the 16-week study at 35 mg/kg/week, a dose equivalent to at least ~190-fold of the 40 mg weekly clinical doses by plasma AUC. Non-dose dependent increases in renal protein excretion (up to 2.2-fold in quantitative urine protein, protein/creatinine ratio or urine albumin) were also observed at 8 and/or 35 mg/kg/week (> ~30 to 190-fold of the 40 mg weekly clinical doses by plasma AUC) at the 16-week scheduled terminal necropsy. However, Similar kidney alterations were not seen at the 6-week interim at any doses or in the 39-week chronic monkey study up to 12 mg/kg/week (> ~200-fold of the 20 mg weekly clinical dose by plasma AUC).

Additional findings related to ASO liver accumulation included increased alanine aminotransferase (ALT), aspartate aminotransferase (AST), and alkaline phosphatase (ALP) at  $\geq$  8 mg/kg/week in the 16and 26-week mouse studies, and were correlated with individual hepatocyte necrosis (minimal to mild) in mouse liver. Those changes were most prominent in the high dose groups (50 and 24 mg/kg/week for the 16- and 26-week studies, respectively). Conversely, no changes in liver enzymes were observed in monkeys from the 39-week toxicity study up to 12 mg/kg/week. In the 16-week monkeys study, increase in ALT was only evident in one early-sacrifice animal at 35 mg/kg/week, and non-statistically significant increases in ALT (< 2-fold of the prestudy baseline) were also observed in the interim- and terminalsacrifice animals at  $\geq$  8 mg/kg/week but showed no microscopic correlates or dose-dependency. Given the spectrum and severity of the test article-related clinicopathologic alterations present in monkeys at doses  $\leq 12 \text{mg/kg/week}$  (> ~100-fold of the 40 mg weekly clinical dose by plasma AUC) during the 39-week treatment phase, none would be regarded to represent an adverse effect (Dorato and Engelhardt 2005; Everds et al. 2013). Considering the monkey to be the most relevant species, these data have characterized the safety profile and established appropriate therapeutic margins for the clinical evaluation of ISIS 703802 in humans.

# 2.3.4 Clinical Experience

Detailed information concerning the clinical studies conducted with ISIS 703802 can be found in the Investigator's Brochure. A summary is included below.

The study drug, ISIS 703802, is being evaluated in Phase 1 in the clinical setting with single doses up to 120 mg and multiple doses up to 60 mg (once per week for 6 weeks). The parent drug ISIS 563580, an unconjugated 2'-MOE modified ASO that has the same base sequence as ISIS 703802, was also evaluated in a blinded, placebo-controlled Phase 1 study.

An interim analysis of ISIS 703802 Phase 1 SAD/MAD Study (ISIS 703802-CS1) was performed in 44 subjects administered single ascending (20, 40 and 80 mg) or multiple ascending doses (10, 20, 40 and 60 mg/week for 6 weeks). Twelve participants were randomly assigned to single-dose groups (9 to activeagent dose groups and 3 to the placebo group) and 32 were randomly assigned to multiple-dose groups (24 to active-agent dose groups and 8 to the placebo group). The main endpoints of the study were safety, tolerability, pharmacokinetics, pharmacodynamics and changes in lipids and lipoproteins. After 6 weeks of treatment, persons in the multiple dose groups treated with ISIS 703802 had dose-dependent reductions in levels of ANGPTL3 protein (reductions of 46.6 to 84.5% from Baseline, P < 0.01 for all doses vs. placebo 1.6%) and in levels of triglycerides (reductions of 33.2 to 63.1% vs placebo 11.4%), LDL cholesterol (1.3 to 32.9% vs placebo 13.6%), very-low-density lipoprotein cholesterol (27.9 to 60.0% vs placebo 4.0%), non-high-density lipoprotein cholesterol (10.0 to 36.6% vs placebo 9.1%), apolipoprotein B (3.4 to 25.7% vs placebo 11.0%), and apolipoprotein C-III (18.9 to 58.8% vs placebo 3.1%). There were no serious adverse events documented during the trial. No protocol-defined injection-site reactions were reported. Of those participants who received the multiple-dose regimen, three reported headache (one who received placebo and two who received ISIS 703802) and three reported dizziness (two who received placebo and one who received ISIS 703802). There was no clinical evidence of prothrombotic effects, bleeding episodes, significant decreases in platelet count or thrombocytopenia, or significant changes in renal function. One subject in the 60 mg weekly dose cohort had an approximately 5 x ULN increase of ALT, without increase in bilirubin and a second subject had an ALT of 88 U/L on Day 36 post treatment which returned to normal range by Day 50 and remained normal until the end of the study. One subject in the 20 mg MAD group was lost to follow-up after 5 doses. There were no other discontinuations during the treatment period (Graham et al. 2017 and data on file).

The pharmacokinetics of ISIS 703802 evaluated in Study ISIS 703802-CS1 showed rapid absorption following SC administration, with median time to maximum plasma concentrations ( $T_{max}$ ) ranging from 1 to 6 hours. Similar  $T_{max}$  values were observed at all dose levels. After reaching  $C_{max}$ , plasma concentrations of ISIS 703802 declined in a multi-phasic fashion with a rapid disposition phase, followed by a slower elimination phase with terminal elimination half-life of 3 to 5 weeks. The peak ( $C_{max}$ ) and total exposure (AUC) after a single SC dose increased approximately dose proportionally from 20 to 40 mg, and greater than dose proportionally from 40 to 80 mg, suggesting more efficient tissue uptake at lower doses. After single and multiple SC doses in the range of 10 to 60 mg, the  $C_{max}$  and AUC increased

approximately dose proportionally. No accumulation based on  $C_{max}$  or AUC was observed after 6 weekly doses.

# 2.3.4.1 ISIS 563580-CS1 Phase 1 SAD/MAD

In a Phase 1 study, ISIS 563580-CS1, healthy volunteers received subcutaneous administration of ISIS 563580, an unconjugated 2'-MOE modified ASO that has the same base sequence as ISIS 703802, from 50 to 400 mg as a single dose, or 100 to 400 mg as multiple doses (8 doses in 36 days). Overall, the safety findings from this study suggest that ISIS 563580 was not associated with any safety concerns. There were 383 adverse events (AE) reported in the ISIS 563580-treated subjects of which 363 (95%) were mild in severity. For the multiple-dose subjects, the most common treatment-emergent adverse events were AEs at the injection site. There was 1 serious adverse event (SAE) in the study of periorbital cellulitis which was considered a medically important event by the Investigator and was also considered unlikely related to Study Drug by the Investigator. Together, the above suggest that ISIS 563580 was well-tolerated at the doses and regimen given, which exceed the dose levels and cumulative exposures to be tested in the current study. There were no clinically-relevant changes in laboratory assessments and the heparin dose of 80 U/kg was well-tolerated in support of the post-heparin procedures. ISIS 563580 produced dose-dependent reductions in plasma ANGPTL3 (up to 93%; group means up to 84%), TG (up to 63%; group means up to 49%) and TC (up to 46%; group means up to 28%) at Day 36 (Brandt et al. 2015).

# 2.4 Rationale for Dose and Schedule of Administration

The Phase 1 program evaluated ISIS 703802 doses of 10 mg, 20 mg, 40 mg and 60 mg given weekly for 6 weeks that were found to be generally well-tolerated and to induce clinically-relevant reductions in lipid biomarkers. The dose proposed for the present study will provide the equivalent drug exposure of 20 mg weekly (80 mg monthly) and is predicted (based on modelling of PK/PD data obtained in Phase 1 study) to result in mean reductions from Baseline in TGs of approximately 63% at steady-state.

Safety data from the available chronic mouse (26-week) and monkey (39-week) studies support once-weekly dosing for chronic administration. The No Adverse Effect Level (NOAEL) for ISIS 703802 in chronic monkey study was determined to be 12 mg/kg/wk.

In healthy volunteers, 703802 achieved an equivalent reduction in ANGPTL3 plasma concentration to that of the unconjugated form, at approximately  $1/10^{\text{th}}$  of the unconjugated ASO (ISIS 563580) dose (Brandt et al. 2015).

# 2.5 Benefit-Risk Assessment

The current study is designed to evaluate the safety and tolerance of ISIS 703802 in patients with FPL. The dose selected is expected to substantially reduce ANGPTL3 and result in a reduction of triglyceride levels, reduction of fat content of the liver and improvement of glycemic control. We do not know if subjects participating in this study would necessarily benefit from the treatment. However, the increased understanding of the effects of ISIS 703802 in this population may potentially result in new treatment options that would ultimately benefit FPL patients. Due to the short duration of this trial any benefit observed is not expected to persist beyond the end of the study.

# 2.5.2 Risk Assessment

The known potential risks to study participants associated with ISIS 703802 are elaborated on in the Guidance to Investigator section of the Investigator's Brochure.

- In preclinical mouse studies, there were increases in ALT and AST and were correlated with increased incidence and/or severity of necrosis of individual hepatocytes (minimal to mild in severity). Those changes were most prominent in the high dose groups and showed no clear progression over time. No increases in liver enzymes were observed in monkeys from the 39-week toxicity study up to 12 mg/kg/week (~200-fold of the 20 mg/week clinical dose by plasma AUC). In the 16-week monkey study, increase in ALT was only evident in 1 early-sacrifice animal at 35 mg/kg/week, no meaningful increase in ALT was observed in the schedule sacrificed animals.
- In the Phase 1 study, there was no elevations in ALT at single dose cohorts up to 120 mg. In multiple dose cohorts, two out of six subjects in the 60 mg weekly dose cohort had a > 2 x ULN increase of ALT, without increase in bilirubin, which was considered a treatment related adverse event (AE) for one by Principal Investigator (PI). There were no other observed clinically significant changes in ALT and liver function in Phase 1 human study (data on file). However, to evaluate and mitigate the potential for liver enzyme abnormalities, regular liver chemistry monitoring and stopping rules are included in the study as specified in Sections 8.5 and 8.6.
- Injection site adverse events, while not considered safety issues, may affect the ability of the subject to tolerate dosing. Injection site adverse events are the most common side effects observed following SC administration of unconjugated 2'-MOE ASOs and are dose and concentration dependent. Erythema is the most prevalent characteristic. Generally, these events are mild and reversible, resolve spontaneously and do not worsen with time. The histologic findings are consistent with a local inflammatory response. Subjects should be informed of the possibility of occurrence of injection site adverse events. Symptomatic interventions such as icing of the injection site or administration of NSAIDs prior to and/or after the SC dosing have been utilized.
- Although no changes in platelet (PLT) counts have been observed in healthy volunteers, mouse or monkey in both sub-chronic and chronic studies with ISIS 703802, reductions in platelet counts to below the lower limit of normal have been observed after administration of other ASOs and some subjects have experienced severe thrombocytopenia following administration of unconjugated 2'-MOE ASOs. To evaluate and mitigate the potential for a reduction in PLT count, monitoring and stopping rules are included in the study as specified in Sections 8.5 and 8.6 (Safety Monitoring Rules and Stopping Rules).
- No significant changes in serum creatinine, electrolytes, BUN, or urinalysis were reported from the interim analysis of the ongoing Phase 1 study (data on file). To evaluate and mitigate the potential for a reduction in renal function, since kidneys are an organ of high distribution for the studied ASO, monitoring and stopping rules are included in the study as specified in Sections 8.5 and 8.6 (Safety Monitoring Rules and Stopping Rules).

While the long term effects of reducing ANGPTL3 as a target with the study drug are not known at this time, there is evidence in literature in humans in whom ANGPTL3 is absent from plasma, due to homozygous or compound heterozygous ANGPTL3 mutations, present a pan-hypobetalipoproteinemia phenotype, with generalized and marked decreases (~50% to 70%) in all apoB-100 containing lipoproteins, including VLDL and LDL, as well as HDL. This clinical phenotype has been termed familial combined hypolipidemia or FHBL2 (Romeo et al. 2009; Musunuru et al. 2010; Martin-Campos et al. 2012; Minicocci et al. 2012; Noto et al. 2012; Pisciotta et al. 2012; Wang et al. 2015). Clinical studies in FHBL2 suggest a trend toward lower glucose and insulin levels and reported decrease in

VLDL. Remarkably, diabetes and cardiovascular disease are reportedly absent from those with homozygous FHBL2 and no adverse clinical phenotype has been reported to date.

# 2.5.3 Overall Assessment of Benefit: Risk

ISIS 703802 has demonstrated the ability to reduce ANGPTL3, APOCIII, and TGs by greater than 60% and LDL-C by more than 30% in the Phase 1 study in healthy volunteers. The objective of this study is to assess the effect of TG lowering in FPL patients. This study will also investigate the potential of ISIS 703802 in improving the insulin resistance and glucose profile, and decreasing liver and visceral fat content in these patients. Although the subjects enrolled in this study will not derive long term benefits due to the short duration of the study, they may derive some short term benefit from improved metabolic health and dietary counselling. The information obtained in the course of this study is critical to further development of ISIS 703802 for FPL patients.

The protocol identifies that potential risks associated with ISIS 703802 treatment will be mitigated by routine monitoring. Thus, exposure of subjects in this study is justified by the anticipated benefits that may be afforded to the wider population of patients by continued development of ISIS 703802.

# 3. EXPERIMENTAL PLAN

# 3.1 Study Design

This is a Phase 2 open-label multiple-dose study of approximately 3 subjects with FPL that will be treated with ISIS 703802. Initially, 3 subject will be enrolled, but enrollment could be increased to 6 subjects, based on safety profile and efficacy observations.

Subjects will be evaluated for study eligibility during Screening and Qualification, which takes place up to 6 weeks prior to Day 1 (the first day of Study Drug administration). During the Screening period, subjects will be advised to maintain routine diet, and remain on a stable regimen of diabetes and lipid medications (if they are already taking any). As part of the Screening period, following 4 weeks of diet run-in, subjects will have a qualification visit and final eligibility assessments will be performed. Subjects on stable diet known to the investigator and followed at the site may go from Screening to qualification without a 4-week diet run-in. At the qualification visit TGs will be measured. MRI and DEXA scan will be obtained during Screening once all other eligibility criteria are met to assess liver fat content. MRI results must be available prior to registration and administration of the first dose of study drug.

Subjects meeting eligibility criteria at qualification will return to the clinic on Day 1 for their first dose of ISIS 703802 by subcutaneous (SC) injection. During the treatment period subjects will receive ISIS 703802 (20 mg) administered every week for 26 weeks.

Subjects will return regularly for outpatient visits throughout the treatment period according to the Schedule of Procedures (Appendix A). The primary safety and efficacy analysis time point is at Week 27.

Subjects will then enter a 13 week Post-Treatment Follow-up Period and will return to the study center for outpatient evaluations according to the Schedule of Procedures (Appendix A).

Blood and urine samples will be collected regularly throughout the study for safety, efficacy, and PK analysis. Appendix B shows a list of analytes required for the study and Appendix C details the PK sample schedule.

# 3.2 Number of Study Centers

This study is planned to be conducted at a single center but will include additional centers if needed.

# 3.3 Number of Subjects

Approximately 3 subjects will be treated in this study. Initially, 3 subject will be enrolled, but enrollment could be increased to 6 subjects, based on safety profile and efficacy observations.

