	k.	Any other medication unless stable at least 4 weeks prior to dosing (occasional or intermittent use of over-the-counter medications will be allowed at Investigator's discretion)
18.		d donation of 50 to 499 mL within 30 days of Screening or of 9 mL within 60 days of Screening
19.		e any other conditions, which, in the opinion of the Investigator or Sponsor would make the patient unsuitable for inclusion, or could

	interfere with the patient participating in or completing the study
Treatment Groups	Single Group, open-label treatment with 20 mg of ISIS 703802 SC weekly
Study Drug Dosage and Administration	The Sponsor will provide ISIS 703802 in a single vial with a concentration of 100 mg/mL 20 mg every week of ISIS 703802 (0.2 mL).
	The study dose of 20 mg (0.2 mL) of ISIS 703802 will be administered every week during the treatment period for a total of 26 weekly doses.
	All doses will be given by SC injection. Self-administration will be allowed after appropriate training of subject and/or caregiver.
Rationale for Dose and Schedule Selection	A 20 mg weekly dose was selected as being the lowest dose that provided maximum TG lowering of approximately 60%, based on the TG lowering effect of ISIS 703802 observed in healthy volunteers with elevated TGs.
Adjustment of Dose or Treatment Schedule	Dose adjustments, including dose interruptions, and/or decreasing the dose and dose frequency may be allowed for safety or tolerability after consultation with the Sponsor Medical Monitor.
Study Visit Schedule and Procedures	Detailed information regarding the study procedures are outlined in Section 6, Appendices A and C.
	The study for an individual subject will generally consist of the following periods:
	
 
An up to 6-week Screening period, including a 4-week diet stabilization phase for subjects not already on a stable diet
 

	
 
A 26-week treatment period during which Study Drug will be administered weekly by SC injection
 

	A 13-week post-treatment follow-up period

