# 4.3 Replacement of Subjects

Due to the small number of subjects participating in the study, subjects who withdraw from the study may be replaced by allowing a new subject to be screened and enrolled. The subjects who withdrew for safety reasons will not be replaced.

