#### **10.2** Sample Size Considerations

There is no statistical rationale for the selected sample size. The sample size is selected based upon prior experience with ISIS 703802 to ensure that the safety, tolerability and efficacy of ISIS 703802 can be explored in an ultra-rare condition before enrolling subjects in a larger study.

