# 10.5 Interim Analysis and Early Stopping Guidelines

Since the study is open labeled no interim analysis will be performed to inform early stopping guidelines.

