# **10.6** Planned Methods of Analysis

Summary tabulations will be provided for disposition, demographic, baseline, efficacy, and safety data as noted in the following sections.

All eCRF data, lab data, and any outcomes derived from the data will be provided in the patient data listings. Patient data listings will be presented for all patients enrolled into the study. Descriptive summary statistics including n, mean, median, standard deviation, standard error, interquartile range (25th percentile, 75th percentile), and range (minimum, maximum) for continuous variables, and counts and percentages for categorical variables will be used to summarize most data.

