#### 10.6.3 Efficacy Analysis

Change at week 27 relative to Baseline will be summarized for:

- Fasting TG
- MTT (plasma glucose, serum insulin, serum C-peptide, FFA, serum ghrelin, GIP, GLP-1 and PYY)
- Glycosylated hemoglobin
- HOMA-IR
- 24-hr glucose
- Adiponectin and leptin
- HFF
- Fat distribution

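### Does the option to grow from 3 to 6 subjects on efficacy observations call for a split Week 27 triglyceride summary?

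*Combined protocol and SAP*

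**What the plan says.** Sections 3.1 and 3.3 share the same sentence: three subjects come first, but "enrollment could be increased to 6 subjects, based on safety profile and efficacy observations". No decision-maker, timing or criterion is given there or elsewhere.

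The treatment description in the Synopsis is "Single Group, open-label treatment with 20 mg of ISIS 703802 SC weekly". The primary endpoint (Section 10.1.1) is percent change in fasting TG at Week 27. TG belongs to the extended lipid panel, which Appendix A schedules at every clinic visit, so results can be seen as they accrue.

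On interim looks, Section 10.5 says only: "Since the study is open labeled no interim analysis will be performed to inform early stopping guidelines". The expansion decision is not mentioned.

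Section 10.6.3 opens with "Change at week 27 relative to Baseline will be summarized for" and lists fasting TG first. Section 10.6 makes all summaries descriptive and adds: "Patient data listings will be presented for all patients enrolled into the study". Section 10.2 states: "There is no statistical rationale for the selected sample size". Section 4.3 lets non-safety withdrawals be replaced: "subjects who withdraw from the study may be replaced by allowing a new subject to be screened and enrolled".

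**The concern.** Letting observed efficacy decide whether more subjects are added, then pooling everyone, is a familiar source of conditional bias. If good early TG results prompted expansion, the first three are favourably selected and the pooled mean of six inherits half of their shift. The later three are not selected in this way, so setting them beside the first three looks like an easy check.

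No test is planned, so type I error is not at issue. What could be affected is how the TG estimate is read. Section 10.2 presents the study as exploration before a larger one, so the Week 27 figure may inform later planning, and a reader would want to know whether the effect also appeared in subjects enrolled after the look. The planned summary does not show that, and nothing requires the date of or reason for the decision to be reported.

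**Working it through.** The plan states no power, SD or effect size, so there is no figure of its own to reproduce.

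**Inputs.** From the documents: n₁ = 3 initial subjects and n₂ = 3 added subjects. Assumed: normal outcomes; between-subject SD of TG percent change of 15, 25 or 35 points; early and late subjects exchangeable; expansion if the first-three Week 27 mean shows a reduction more than c points better than the true mean.

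**Formulas.** Let s₃ = SD/√3 = 8.7, 14.4, 20.2; a = c/s₃; λ = φ(a)/(1 − Φ(a)). Let ρ be the correlation between whatever drives the decision and the first-three Week 27 mean. Positive bias means the reduction is overstated.

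- Pooled bias given expansion = ½ · ρ · s₃ · λ
- Standard error (SE) of an unselected six-subject mean = SD/√6
- Root mean squared error (RMSE) of the pooled mean given expansion (ρ = 1) = √{[s₃²(1 + aλ) + s₃²]/4}
- RMSE of the added three alone = s₃

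For c = 0, λ = 0.798, so the bias at ρ = 1 is 0.5 × 0.798/√3 = 0.230 SD. Simulation of 2,000,000 trials gave 0.461 SD for the first three, 0.231 SD pooled and 0.001 SD for the later three.

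| | SD 15 | SD 25 | SD 35 |
|---|---|---|---|
| Pooled bias, c = 0, ρ = 1 | 3.5 | 5.8 | 8.1 |
| Pooled bias, c = 0, ρ = 0.7 | 2.4 | 4.0 | 5.6 |
| Pooled bias, ρ = 0 | 0 | 0 | 0 |
| Pooled bias, c = 10, ρ = 1 | 7.1 | 9.3 | 11.5 |
| Chance of expansion, c = 10 | 12% | 24% | 31% |
| SE of unselected mean of six | 6.1 | 10.2 | 14.3 |
| Pooled RMSE, c = 0, ρ = 1 | 6.1 | 10.2 | 14.3 |
| Pooled RMSE, c = 10, ρ = 1 | 8.6 | 12.3 | 16.2 |
| RMSE of added three alone | 8.7 | 14.4 | 20.2 |

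**Accuracy.** At c = 0, a = 0 and the pooled RMSE reduces to √(s₃²/2) = SD/√6. The match with the unselected SE is therefore exact: the bias is offset by the smaller variance of a truncated first-stage mean. Even under the stricter trigger the pooled mean has lower RMSE than the added three alone.

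**Direction.** If expansion follows weak results, the c = 0 biases reverse sign. Averaged over trials that expand and trials that stop at three, the bias of the final estimate at c = 0, ρ = 1 is −½ · s₃ · φ(0) = −0.115 SD, that is −1.7, −2.9 and −4.0 points: the opposite of the conditional figure.

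**What a split could show.** Under c = 0, ρ = 1 the expected gap between the two group means is 0.798 · s₃ = 6.9, 11.5, 16.1 points. Its standard deviation is s₃ · √(2 − 2/π) = 10.1, 16.9, 23.6 points, larger than the gap itself. Given m₁ > 0 (means measured from the truth), m₁ > m₂ covers 135 of the 180 degrees in the half-plane. The first group therefore looks better with probability 0.75 under full selection, against 0.50 under none. A 95% t interval has half-width 2.48 SD for three subjects and 1.05 SD for six; at SD 25 that is 62 and 26 points.

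**The case for a change.** The strongest case for a change is that it costs almost nothing. It would need no new data, would apply only if expansion occurred, and would leave the flexibility in Sections 3.1 and 3.3 untouched. Listings alone do not settle the matter: they give eCRF data, laboratory data and derived outcomes, but a sponsor's decision date is none of these. Because Section 4.3 allows replacements, subject order is not a safe proxy for enrolment before or after the look. With an SD of 15 and the stricter trigger, the bias of 7.1 points exceeds the SE of 6.1.

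Part of this stands. The decision date and reason are not promised anywhere, and without them a reader cannot tell a TG-driven expansion from one made on safety grounds. That argues for a statement of fact in the study report; it does not make the analysis in Section 10.6.3 wrong.

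The split table itself is harder to defend. Treating the later group as an unbiased check requires early and late subjects to be exchangeable. Section 3.2 allows further centers. Inclusion criterion 5 admits TG of at least 500 mg/dL, or 200 to below 500 mg/dL with genetic or family-history criteria, so later subjects may differ at baseline. Replacement adds selection through withdrawal. Differences between two groups of about three would invite over-reading, whereas the individual listings show more than two such means.

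**Conclusion.** The concern describes a real mechanism, but no change to the plan follows. The bias of 3.5, 5.8 or 8.1 points rests on an assumed SD and on expansion depending wholly on better-than-true Week 27 TG in the first three subjects. The protocol says neither: its wording covers safety as well as efficacy, and Section 10.6.3 also lists HbA1c, HOMA-IR, mixed-meal responses, hepatic fat fraction and fat distribution. Depending on the actual reason, the shift could be positive, zero or negative.

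Under the main trigger the pooled mean loses no accuracy relative to an unselected mean of six, and it remains the better main summary, which is what the plan already provides. In an untested, descriptive study of about three to six patients, with every value listed, what remains is missing detail about when and why enrolment grew. That can be stated in the report if expansion happens, and it changes no result.
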